13.3.5. Pharmacodynamic Analyses

Blood samples for assessment of pharmacodynamic parameters such as EPO will be obtained in conjunction with PK samples, before (pre-dose) and 6 hours after study drug administration at the Week 1 visit and only before study drug administration at the Week 3 and 5 visits.

The value, change from baseline, and percent change from baseline will be listed and summarized for each scheduled time-point during the study for each of the pharmacodynamic parameters.

To investigate the effect of these potential biomarkers on efficacy, the association of baseline pharmacodynamic parameters with ORR and PFS will be investigated using exploratory multivariate techniques, subgroup analyses, and regression modeling.

The summaries will be based on the Safety Analysis Set. The exploratory analyses will be performed for the Efficacy Analysis Set.

13.3.6. Safety Analyses

Safety data analysis will be conducted for all patients in the Safety Analysis Set. Analyses will consist of data summaries for AEs/SAEs, clinical laboratory parameters, vital signs, and ECGs.

13.3.6.1. Adverse Events

Adverse events occurring from the time the patient gives consent but prior to study drug administration will be captured on the Medical History CRF. All AEs occurring on or after the first day of treatment and within 30 days after administration of the last dose of study drug will be considered to be a treatment-emergent adverse event (TEAE).

08LO5Z

Adverse events will be coded according to the latest Version of the Medical Dictionary for Regulatory Activities (MedDRA). The severity of AEs will be coded according to NCI CTCAE 4.03. Treatment-related AEs are AEs that are not stated as unrelated to PT2385.

An overall summary of TEAEs will summarize the number (%) of patients with at least 1 of the following.

- TEAE
- PT2385 related TEAE
- Grade 3 or higher TEAE
- Grade 3 or higher PT2385 related TEAE
- Grade 5 TEAE
- SAE
- Leading to discontinuation of PT2385

Summaries of the following TEAEs will be provided by system organ class and preferred term.

- All TEAEs
- TEAEs by maximum severity
- TEAEs grade 3 or higher
- PT2385 related TEAEs
- Grade 3 or higher PT2385 related TEAE
- Serious TEAEs
- TEAEs that led to permanent discontinuation of study of PT2385

A summary of the number of deaths within 30 days of administration of the last dose of study drug and deaths more than 30 days after administration of the last dose of study drug will be provided.

Listings will be provided of AEs identified as treatment-limiting toxicity, deaths, SAEs, and AEs leading to discontinuation of PT2385 tablet treatment.

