7.2.3. Patient Withdrawal Criteria

Patients have the right to withdraw from the study or study treatment at any time for any reason. The Investigator may discontinue a patient from the study or study treatment for any of the following reasons:

- Disease progression per RECIST 1.1
- Occurrence of an AE, development of an intercurrent illness/condition, or change in patient's condition that leads the Investigator to be concerned about the patient's welfare
- Treatment-limiting toxicity or intolerable toxicity
- Noncompliance with study procedures
- Failure to comply with study drug administration instructions, to return for follow up, or to meet other requirements of the study
- Pregnancy in a female patient during the study
- Death
- Withdrawal of consent

The reason for a patient's withdrawal from the study or study treatment will be recorded in the case report form (CRF). Patients who withdraw from study participation for any reason may not re-enter the study at any time.

Patients who discontinue from study treatment will be asked to complete the early termination and safety follow-up procedures according to the Schedule of Events, Appendix 1. During the safety follow-up the patient should be evaluated for continuation or resolution of any treatment-related AEs/SAEs

Long-term follow-up will begin at the time a patient discontinues study treatment for any reason and will continue for up to 3 years following completion of enrollment in the study or until the patient withdraws consent or dies.

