12.2. Adverse and Serious Adverse Events

12.2.1. Definition of Adverse Events

12.2.1.1. Adverse Events

An AE is defined as any untoward medical occurrence in a patient regardless of its causal relationship to study treatment. An AE can be any unfavorable and unintended sign (including any clinically significant abnormal laboratory test result), symptom, or disease temporally associated with the use of the study drug, whether or not it is considered to be study drug related. Included in this definition are any newly occurring events and any previous condition that has increased in severity or frequency since the administration of study drug. Disease progression is a study endpoint and consequently, should not be reported as an AE. However, if a patient dies from disease progression with no other immediate causes, "disease progression" should be reported as an SAE (Section 12.7).

All AEs that are observed or reported by the patient during the study (from the time of administration of the first dose of study drug until the final visit indicated in Appendix 1) must be reported, regardless of their relationship to study drug or their clinical significance.

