12.2.1.2. Serious Adverse Events

An SAE is any AE occurring at any dose and regardless of causality that meets any of the following criteria.

- Results in death
- Is life-threatening
- Requires inpatient hospitalization > 24 hours or prolongation of existing hospitalization
- Results in persistent or significant incapacity or substantial disruption of the ability to conduct normal life functions
- Is a congenital anomaly or birth defect in an offspring of a patient taking study drug
- Is an important medical event

The term "life-threatening" refers to an event in which the patient is at immediate risk of death at the time of the event. The term does not refer to an event that hypothetically might cause death if it were more severe.

Important medical events are those that may not meet any of the criteria defined above; however, they may be considered serious when, based upon appropriate medical judgment, they may jeopardize the patient and may require medical or surgical intervention to prevent one of the other outcomes listed in the SAE definition.

Pregnancy is not considered an AE; however, information will be collected for any pregnancies that occur during the study (from the time the first dose of study drug is administered until the final visit indicated in Appendix 1). Certain pregnancy outcomes will require submission as an SAE.

The Investigator is responsible for reporting to Peloton Therapeutics or designee all AEs and SAEs that are observed or reported by the patient during the study (from the time the first dose of study drug is administered until the final visit indicated in Appendix 1), regardless of their relationship to study drug or their clinical significance. All SAEs reported or observed during the study must be followed to resolution or until the Investigator deems the event to be chronic or the patient to be stable. Peloton Therapeutics or designee may contact the Investigator to obtain additional information on any SAE that has not resolved at the time the patient completes the study.

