12.6. Recording Adverse Events

All conditions present before administration of the first dose of study drug should be documented as medical history. All drug-related (possible or probable, see Section 12.4) AEs and abnormal laboratory test results reported or observed during the study must be followed to resolution (either return to baseline or within normal limits). All other AEs will be followed through the final visit indicated in Appendix 1. Information to be collected includes type of event, date of onset, date of resolution, Investigator-specified assessment of severity and relationship to study drug, seriousness, as well as any action taken.

While an AE is ongoing, changes in the severity (e.g., worsening and improving) should be noted in the source documents but, when documenting the AE, only the total duration and greatest severity should be recorded in the CRF. AEs characterized as intermittent require documentation of onset and duration.

AEs resulting from concurrent illnesses, reactions to concurrent illnesses, reactions to concurrent medications, or progression of disease states must also be reported. Preexisting conditions (present before the start of the AE collection period) are considered concurrent medical conditions and should NOT be recorded as AEs. However, if the patient experiences a worsening or complication of such a concurrent condition, the worsening or complication (except disease progression) should be recorded as an AE. Investigators should ensure that the AE term recorded captures the change in the condition (e.g., "worsening of...").

Each AE should be recorded to represent a single diagnosis. Accompanying signs (including abnormal laboratory test values or ECG findings) or symptoms should NOT be recorded as additional AEs. If a diagnosis is unknown, sign(s) or symptom(s) should be recorded as an AE(s). Changes in laboratory test values or ECG parameters are only considered to be AEs if they are judged to be clinically significant (i.e., if some action or intervention is required or if the Investigator judges the change to be beyond the range of normal physiologic fluctuation). If abnormal laboratory test values or ECG findings are the result of pathology for which there is an overall diagnosis (e.g., increased creatinine levels in renal failure), only the diagnosis should be reported as an AE.

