20. APPENDICES

- Appendix 1 Schedule of Events
- Appendix 2 ECOG Performance Status
- Appendix 3 RECIST 1.1 Summary
- Appendix 4 Evaluation of Non-Renal VHL Related Disease
- Appendix 5 New York Heart Association Functional Classification
- Appendix 6 Partial List of Strong CYP2C19 and CYP3A4 Inhibitors
- Appendix 7 Partial List of Substrates of CYP3A4, CYP2B6, CYP2C9, and CYP2C19

Appendix 1	Schedule of Events
------------	--------------------

	Treatment Period				Post-Treatment Period/ Early Termination		
Assessment	Screening (Day -28 to Day -1)	Week 1 ¹ (Day 1)	Weeks 3 and 5 ¹ (± 1 Day)	Weeks 9, 13, 17, and Every 4 Weeks ¹ (± 2 Days)	Extended Treatment ² Every 12 Weeks (± 1 Week)	Safety Follow-Up 28 Days After Last Dose of Study Drug Taken (± 7 Days)	Long Term Follow-up (every 6 months) ¹⁶
Informed Consent	Х						
Assess Inclusion/Exclusion	Х						
Demographics and Medical	Х						
Physical Examination ³	Х	Х	Х	Х	Х	Х	
Vital Signs ⁴	Х	X 4	X	Х	Х	Х	
Weight	Х	Х	Х	Х	Х	Х	
Height	Х						
ECOG	Х	Х	Х	Х	Х	Х	
Dispense/Collect Study Drug		Х	Х	Х	Х		
Hematology ⁵	Х	Х	Х	Х	Х	Х	
Serum Chemistry ⁶	Х	Х	Х	Х	Х	Х	
PT, aPTT, INR	Х						
Iron Panel ⁷	Х	Х	Х	Х		Х	
Urinalysis ⁸	Х	Х	Х	Х	Х	Х	
Pregnancy Test ⁹	Х	Х	Х	Х	Х	Х	
ECG ¹⁰	Х	X^{10}	X^{10}	X^{10}			
Tumor Assessment ¹¹	Х			X ¹¹	Х		
Pharmacokinetic Sample ¹²		Х	Х	Х			
Pharmacodynamic Sample ¹³		Х	Х	Х			
Assessment of Male Fertility ¹⁴	Х			X ¹⁴		X ¹⁴	
Tissue Sample Collection ¹⁵	Х						
Adverse Events		Х	Х	Х	Х	Х	
Concomitant Medications	Х	X	X	X	Х		
Study Drug Administration				X			
Patient Status ¹⁶							X

ECG = electrocardiogram; ECOG = Eastern Cooperative Oncology Group; PT/aPTT = prothrombin time/activated partial thromboplastin time.

Peloton Therapeutics, Inc. 08LQCONFIDENTIAL

- 1. Assessments are to be done on Day 1 of each visit week. For the Weeks 3 and 5 visits, assessments may be ± 1 day; for the Week 9, 13, and 17 visits and for visits every 4 weeks thereafter, assessments may be ± 2 days.
- 2. For patients deriving clinical benefit at 1 year and continuing to take study drug after 1 year, visits will be conducted at 12-week intervals.
- 3. Funduscopic exams must be performed at Screening, Baseline, and every 12 weeks during the treatment period.

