- 11. Tumor assessment including non-contrast or contrast computed tomography (CT), or magnetic resonance imaging (MRI) will be obtained at screening and within 7 days before the Week 13 visit, and every 12 weeks thereafter (e.g., before the visits for Weeks 25, 37, etc.).
- 12. At the Week 1 visit, patients will take their morning dose of PT2385 in the clinic and will have 4 mL of blood drawn for pharmacokinetic (PK) assessment before (pre-dose) and 6 hours after study drug administration. At the Week 3, 5, 9, 13, and 17 week visits, patients will take their morning dose of PT2385 in the clinic. The blood sample for PK assessment is to be obtained before study drug administration on these days.
- 13. Blood samples for analysis of pharmacodynamic effects of PT2385 (e.g., erythropoietin) will be obtained in conjunction with PK samples, before (pre-dose) and 6 hours after study drug administration at the Week 1 visit and only before study drug administration at the Weeks 3, 5, 9, 13 and 17 visits; patients should not take their dose of PT2385 until after this blood collection has occurred at these visits. Two whole blood samples will be collected at the Week 1 visit only for sequencing of genes encoding proteins that may be involved in regulating PT2385 metabolism.
- 14. Tests (orchidometry, semen analysis, and measurement of testosterone, follicle stimulating hormone, luteinizing hormone, and inhibin B levels) are to be conducted at Screening, the Week 17 visit, and 13 weeks after last study drug administration for those male patients for whom a clinically significant effect on fertility was seen at Week 17.
- 15. Archival tumor tissue samples will be obtained whenever possible from all patients. Additionally, fresh tissue sample will be obtained from consenting patients in whom tumor tissue is accessible (patients who undergo tumor excision during the study).
- 16. Long-term follow-up may be accomplished via an in person visit or telephone. The patient will be questioned about the following since their last study visit or telephone contact: medical history, surgical history, disease status, and survival status.

Peloton Therapeutics, Inc. 08LQCONFIDENTIAL

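### TEAEs are defined to 30 days after the last dose, but AE collection can close as early as day 21, so late-onset TEAEs can be missed; the effect is probably small.

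*Combined protocol and SAP*

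**What the plan says.** **Analysis window.** Section 13.3.6.1 starts the TEAE period on the first treatment day and sets its end as follows: AEs "within 30 days after administration of the last dose of study drug will be considered to be a treatment-emergent adverse event (TEAE"). The overall summary in the same section includes SAEs and Grade 5 TEAEs.

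**Collection window.** Section 12.2.1.1 requires AEs to be reported "from the time of administration of the first dose of study drug until the final visit indicated in Appendix 1". Section 12.2.1.2 repeats this for AEs and SAEs together: "from the time the first dose of study drug is administered until the final visit indicated in Appendix 1". Neither section gives a number of days. Section 12.6 uses the same end point for AEs not considered drug-related: "All other AEs will be followed through the final visit indicated in Appendix 1".

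**Visit schedule.** In the Appendix 1 grid the Adverse Events row is last marked in the column headed "Safety Follow-Up 28 Days After Last Dose of Study Drug Taken (± 7 Days"). The row is blank under long-term follow-up. Note 16 limits that contact to questions on "medical history, surgical history, disease status, and survival status".

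**Deaths.** Section 13.3.6.1 also plans a table with two categories: "deaths within 30 days of administration of the last dose of study drug and deaths more than 30 days after administration". Section 7.2.3 gives a separate source for these: "Long-term follow-up will begin at the time a patient discontinues study treatment for any reason and will continue for up to 3 years", counted from the completion of enrollment.

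**The concern.** The period in which AEs are collected and the period over which they are analyzed are set by different sections, and they do not match. A site that follows the schedule to the day still stops asking about new events 2 days before the TEAE window closes. A site that uses the full tolerance can stop 9 days before. No section requires AE collection to day 30.

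Three things are at stake:

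- Onsets after the visit but inside the window can be missed from the TEAE tables, including those for serious and Grade 3 or higher events. Safety is a secondary objective and enrollment is capped at 50, so one missed patient moves a reported percentage by 1/50 = 2 points, or more if fewer are treated.
- Post-treatment observation runs from 21 to 35 days depending on the visit date, while the tables present one fixed 30-day window.
- Two safety outputs for the same 30 days rest on different sources. Deaths within 30 days can draw on survival follow-up. Grade 5 TEAEs depend on AE reporting that may already have closed. The two can disagree.

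**Working it through.** The plan states no derived figure on this point, so there is nothing to reproduce. The check is date arithmetic, with all days counted from the last dose.

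**Inputs**

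- End of the TEAE window: day 30 (Section 13.3.6.1).
- Last AE-marked visit: day 28 ± 7 (Appendix 1).
- End of AE and SAE reporting: the final visit in Appendix 1 (Sections 12.2.1.1 and 12.2.1.2), read here as that Safety Follow-Up visit.

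**Permitted visit days.** Earliest 28 − 7 = 21; latest 28 + 7 = 35; so 35 − 21 + 1 = 15 possible days.

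**Uncovered days** for a visit on day v: u(v) = max(0, 30 − v).

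- Earliest visit: u(21) = 9
- Nominal visit: u(28) = 2
- Visits on days 30 to 35: u = 0

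Visits on days 21 to 29, which are 9 of the 15 permitted days, leave part of the window uncovered. If visits were spread evenly over the 15 days (an assumption; the protocol gives no distribution), the mean gap would be (9 + 8 + … + 1)/15 = 45/15 = 3.0 days.

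**Share of time at risk.** The TEAE window starts on the first day of treatment, so the gap should be set against treatment time plus 30 days. For w weeks of treatment and a constant event rate, the share is u/(7w + 30). Treatment durations and the constant rate are assumptions.

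| Weeks treated | Days at risk | Worst case (9 days) | Nominal (2 days) | Even spread (3 days) |
|---|---|---|---|---|
| 12 | 114 | 7.9% | 1.8% | 2.6% |
| 24 | 198 | 4.5% | 1.0% | 1.5% |
| 52 | 394 | 2.3% | 0.5% | 0.8% |
| 104 | 758 | 1.2% | 0.3% | 0.4% |

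**Deaths.** Long-term follow-up starts at treatment discontinuation and asks for survival status every 6 months, so it covers the days between the safety visit and day 30. The gap for the death table is about 0 days.

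**The case against.** **The final visit is not named.** It could be read as the last long-term contact, which asks about medical and surgical history since the previous one. On that reading collection would run well past day 30. The wording is indeed loose, but the schedule points the other way: the AE row is blank in that column, and Section 7.2.3 places the evaluation of treatment-related AEs and SAEs in the safety follow-up. If the long-term contact was intended, the text still needs correcting.

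**Drug-related AEs are followed until they resolve (Section 12.6).** That rule concerns events already reported. It does not capture new onsets after the visit.

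**Little would be missed.** Section 4.1.2.4 gives a half-life of 17 hours, so day 21 is 21 × 24/17 ≈ 30 half-lives after the last dose, and new drug-related onsets on days 21 to 30 may be rare. The study has one arm and its safety summaries are descriptive, so no comparison between arms can be distorted. Differences in treatment duration will far exceed a few days of visit tolerance. All of this stands and keeps the point minor. It does not remove the conflict, because the TEAE definition covers all AEs in the window, related or not.

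**Pregnancy.** A reader might extend the point to pregnancy reporting, since Section 12.2.1.2 ends it at the same visit while contraception is required for 30 days. Section 12.8.2 separately requires immediate reporting of any pregnancy associated with exposure, so the documents give that extension little support.

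**Conclusion.** The mismatch is real for AEs and SAEs, on the better reading of the final visit. A visit on days 21 to 29 ends collection before the TEAE window closes, by 2 days at the nominal visit and by 9 at most. Late-onset TEAEs can therefore be missed, and follow-up length varies with the visit date. Visits on days 30 to 35 leave no gap. The primary endpoint is untouched.

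Three stronger readings are not supported:

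- **That deaths are cut off too.** The death table draws on survival status from long-term follow-up and has its own category beyond 30 days. The exceptions are patients who withdraw consent and any who stop treatment more than 3 years after enrollment completes.
- **That TEAE counts are biased downward as a matter of fact.** The documents give no event rate after the last dose. They show only that an under-count is possible.
- **That 30% of the window is lost.** The ratio 9/30 is the worst case set against the post-dose tail alone. Against the whole TEAE period, at a constant event rate, the worst case is about 7.9% for an assumed 12 weeks of treatment and 2.3% for 52 weeks.

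This is a low-severity conflict between stated rules, with a probably small effect.

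**What to change.** Reconcile Sections 12.2.1.1, 12.2.1.2 and 13.3.6.1 with Appendix 1 so that AE and SAE collection reaches day 30 after the last dose for every patient. Either of two changes does this:

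1. Set the Safety Follow-Up window in Appendix 1 so that the visit that closes AE collection cannot fall before day 30.
2. Keep the present visit window and state in Sections 12.2.1.1 and 12.2.1.2 that AEs and SAEs are collected to day 30, with a telephone contact on or after day 30 when the visit took place before it.

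In both cases, name the visit or contact that ends AE collection, so that Section 12.6 and the Appendix 1 grid point to the same day. Uncovered time then falls to 0 days.

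The cost is a wording change to the visit window, or at most one telephone call for each patient seen early.

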12.4. Assessment of Causality

The Investigator must use the following classifications and criteria to characterize the relationship or association of PT2385 in causing or contributing to the AE:

Unrelated: This relationship suggests that there is no association between the study drug and the reported event.

Unlikely: This relationship suggests that the temporal sequence of the event with study drug administration makes a causal relationship improbable and/or other factors also provide plausible explanations.

Possible: This relationship suggests that treatment with the study drug caused or contributed to the AE. That is, the event follows a reasonable temporal sequence from the time of study drug administration, and/or, follows a known response pattern to the study drug, but could have been produced by other factors.

Probable: This relationship suggests that a reasonable temporal sequence of the event with study drug administration exists and, based upon the known pharmacological action of the drug, known or previously reported adverse reactions to the drug or class of drugs, or judgment based on the Investigator's clinical experience, the association of the event with study drug administration seems likely.

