12.7. Reporting Serious Adverse Events

Any AE that meets the previously described criteria for "serious" must be reported to the Sponsor's designee within 24 hours from the time when site personnel first learn about the event. To report the SAE, fax or email the completed SAE form to SCRI Development Innovations Pharmacovigilance Department (contact information listed in Table 4) within 24 hours of awareness. For questions regarding SAE reporting, SCRI Development Innovations Safety personnel can be contacted by phone, fax or email, see Table 4.

Table 4Serious Adverse Event Reporting Contact Information

The Investigator must continue to follow the patient until the SAE has subsided or until the condition becomes chronic in nature, stabilizes (in the case of persistent impairment), or the patient dies. Within 24 hours of receipt of new information, the updated follow-up SAE form, along with any supporting documentation (e.g., patient discharge summary or autopsy reports), should be faxed to SCRI Development Innovations Pharmacovigilance Department (Table 4).

Peloton Therapeutics or designee will notify regulatory agencies of any fatal or life-threatening unexpected events associated with the use of the study drug as soon as possible but no later than 7 calendar days after the initial receipt of the information. Initial notification will be followed by a written report within the timeframe established by the appropriate regulatory agency. For other SAEs that do not meet the fatal or life-threatening unexpected criteria, but are deemed by the Investigator to be associated with the use of the study drug (that is, "possible" or "probable" in causality assessment), Peloton Therapeutics or designee will notify the appropriate regulatory agencies in writing within the timeframe established by those regulatory agencies. Peloton Therapeutics or designee will provide copies of any reports to regulatory agencies regarding serious and unexpected SAEs to the Investigators for their information and submission to their institutional review board (IRB), as appropriate.

Principal Investigators are responsible for informing their IRB of any SAEs at their site, as appropriate. Serious AE correspondence with regulatory authorities or IRBs must be submitted to Peloton Therapeutics or designee for recording in the study file.

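### The PT2385-related tables count Unlikely and unrated events as related, although the protocol elsewhere maps its causality scale to related as Possible or Probable only

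*Combined protocol and SAP*

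**What the plan says.** Section 12.4 requires the investigator to place each adverse event at one of four levels.

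- Unrelated: "This relationship suggests that there is no association between the study drug and the reported event".
- Unlikely: the timing "makes a causal relationship improbable and/or other factors also provide plausible explanations".
- Possible: a causal or contributing role for the drug is suggested, though something else may explain the event.
- Probable: "the association of the event with study drug administration seems likely".

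Two later sections divide this scale in two. Section 12.6, on which events are followed to resolution, refers to "All drug-related (possible or probable, see Section 12.4) AEs". Section 12.7, on written notice to regulators of serious events outside the fatal or life-threatening unexpected group, covers those "deemed by the Investigator to be associated with the use of the study drug" and names Possible and Probable in parentheses as what that means.

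Section 13.3.6.1 governs the tables and divides the scale elsewhere: "Treatment-related AEs are AEs that are not stated as unrelated to PT2385". That rule feeds four planned outputs: PT2385-related TEAEs and Grade 3 or higher PT2385-related TEAEs, each in the overall summary and by system organ class and preferred term.

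The synopsis, under Safety Assessments in the statistical methods, also promises a summary of patients with adverse events by relationship and severity. It does not say how many relationship levels that summary will show.

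**The concern.** An event that the investigator judged causally improbable would be tabulated as PT2385-related. The same event would fall outside what Section 12.6 calls drug-related. A reader of the study report who knows the 12.4 scale and the 12.6 mapping would reasonably take a related rate to mean Possible or Probable, and would misread the table.

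This matters more than usual because the study has one arm and no reference therapy. With no comparator rate, investigator attribution is the main way to separate drug effects from background events. The related and Grade 3 or higher related percentages are likely to be quoted on their own.

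Section 13.3.6.1 lists no table by the four levels, so the planned tables may not show how much of the related count comes from Unlikely ratings.

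**Working it through.** The documents state no related-event rate, so there is no plan figure to reproduce. The check compares the definitions and then works out what one patient contributes.

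**Inputs from the documents**

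- Scale: four levels (12.4).
- Mapping for follow-up and for regulatory notice: Possible or Probable (12.6, 12.7).
- Mapping for tables: anything not Unrelated (13.3.6.1).
- Denominator: Safety Analysis Set, meaning enrolled and dosed at least once (13.2, 13.3). Planned enrolment is 50 (6.2). I assume all 50 are dosed.

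**Side by side**

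| Rating | 12.6 / 12.7 | 13.3.6.1 |
|---|---|---|
| Unrelated | no | no |
| Unlikely | no | yes |
| Possible | yes | yes |
| Probable | yes | yes |
| Not recorded | not addressed | yes, read literally |

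The set {Possible, Probable} lies wholly inside {Unlikely, Possible, Probable, not recorded}. The 13.3.6.1 count is therefore never below the Possible/Probable count. It is higher as soon as one patient has an Unlikely or unrated event and nothing rated Possible or Probable.

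**Contribution per patient**

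The overall summary counts patients with at least one event, so each such patient adds 1/50 = 2.0 percentage points. In the Grade 3 or higher row the same holds for a patient whose only Grade 3 or higher events outside Unrelated are Unlikely or unrated.

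**Illustration of size (all inputs assumed)**

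Let each patient have k events with independent ratings, a share r rated Possible or Probable and a share u rated Unlikely. The proportion of patients with at least one related event is

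- Possible/Probable: 1 − (1 − r)^k
- Not Unrelated: 1 − (1 − r − u)^k

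With k = 3, r = 0.30, u = 0.10:

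- 1 − 0.70³ = 65.7%
- 1 − 0.60³ = 78.4%
- excess 12.7 points

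With k = 5 and the same shares:

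- 1 − 0.70⁵ = 83.2%
- 1 − 0.60⁵ = 92.2%
- excess 9.0 points

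Over k = 1, 3, 5, r = 0.10 or 0.30 and u from 0 to 0.30, the excess runs from 0 (at u = 0) to 51.3 points (r = 0.10, u = 0.30, k = 3 or 5). The range is this wide because nothing in the documents fixes k, r or u.

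The example also shows that a ratio of events does not carry over to the reported percentages. With r = 0.30 and u = 0.10, related events rise by a factor of 0.40/0.30 = 1.33. Patients with a related event rise by 78.4/65.7 = 1.19 at k = 3 and by 92.2/83.2 = 1.11 at k = 5. A patient with both an Unlikely and a Possible event counts once under either rule.

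**The case against.** The strongest reply is that the three sections serve different purposes. Section 12.6 says which events are followed to resolution, 12.7 says which serious events trigger a written notice, and only 13.3.6.1 governs tabulation. Separating no association from everything else is a coherent rule. It errs toward attributing events to the drug, which can be defended when there is no comparator. The rating is also kept: 12.6 collects it for each event, 13.3 promises by-patient listings, all-causality tables stand beside the related ones, and the synopsis plans a summary by relationship. Section 13 leaves the detail to an SAP due before database lock.

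Most of this stands. A broad count may be deliberate, and no information is lost from the database. But the protocol does not say that the broad rule is a convention, does not label it as one, and does not reconcile it with its own reading of the scale in 12.6. Listings allow the narrower count only by hand. The synopsis summary helps only if it shows all four levels, which is not specified. In an open-label study the mapping is better settled before the ratings accumulate than shortly before lock.

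A reader might draw three stronger conclusions that the documents do not support.

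- **The related rates are inflated by some definite factor.** No causality distribution is given, and an event ratio is not a patient percentage.
- **The tables ought to match the events handled under 12.6 and 12.7.** Section 12.6 also covers abnormal laboratory results and is not tied to the 30-day TEAE window. The Possible/Probable wording in 12.7 applies to a subset of serious events. The sets would differ under either definition, and nothing requires them to agree.
- **The table rule alters the treatment-limiting toxicity assessment in Section 6.4.** That section neither cites nor depends on 13.3.6.1.

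**Conclusion.** The point holds as an inconsistency in definition that affects four descriptive safety outputs. The direction is certain: the tabulated related counts are at least as large as the Possible/Probable counts. The size is 2 percentage points for each affected patient if 50 are dosed. The total cannot be determined from the documents and is zero if no patient is affected. The percentages in the illustration rest on assumed event numbers and rating shares, and on independent ratings.

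No efficacy result, sample size or error rate depends on this definition. It should be corrected because the change is cheap and alters how a headline safety rate is read.

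**What to change.** In Section 13.3.6.1, replace the current sentence with a rule to this effect: *PT2385-related means a relationship of Possible or Probable under Section 12.4; a TEAE with no recorded relationship is counted as related.* Use it in all four related-TEAE outputs and carry it into the SAP.

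Add a separately labelled row for the broader count (every TEAE not rated Unrelated). Because missing ratings stay in the headline count, the two rows will differ only by patients whose sole events outside Unrelated are Unlikely.

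Specify that the relationship summary promised in the synopsis shows all four levels, plus any missing ratings.

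The cost is a sentence and an extra row, with no new data. The headline related count becomes less conservative, but the broad row and the planned all-causality tables keep the conservative view in sight.
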